### 8.3 Rescreening of Subjects

Rescreening of subjects is not allowed in this study.

## 9 TREATMENTS ADMINISTERED

### 9.1 Investigational Product(s)

*Test Product(s):* [REDACTED] (LID220365)

*Comparator Product(s) (If applicable):* DT1 (LID006961)

**Table 9–1**

**Test Product**

Test Product	[REDACTED] spherical soft contact lenses [REDACTED] LID220365)
Manufacturer	Alcon Laboratories, Inc. [name] USA
Indication for use and intended purpose in the current study	The investigational daily disposable contact lenses are indicated for the optical correction of refractive ametropia (myopia and hyperopia) in phakic and aphakic persons with nondiseased eyes with up to approximately 1.5 D of astigmatism that does not interfere with VA.
Product description and parameters available for this study	

• Material: delefilcon A

• Water content: 33%

• Power range: -1.00 to -6.00 D, 0.25 D steps

• Base curve (mm): 8.5

• Diameter (mm): 14.1

Formulation	Please refer to IB.
Usage	

• Wear:

○ Daily Wear

○ Contralateral

• Replacement period: Daily Disposable

	

• Exposure: daily for approximately 4 days total duration

• Lens Care: N/A

Number/Amount of product to be provided to the subject	Subject will be dispensed study lenses at Visit 1. Spare lens(es) will be provided to the subject.
Packaging description	Blister foil pack
Labeling description	
Lens Foil label includes:
 

- material name and identifier

- base curve

- diameter

- packing solution

- power

- lot number

- expiration date

- content statement

- investigational device statement

- sponsor information

- country of origin

 
• Provided in packages of approximately 40 lenses per power, identified with the following at a min:
 

- a color coded label stating the protocol number

- material identifier

- power

- an investigational use only statement

- tracking number

Training and/or experience requirements for device	No additional training or experience is required to administer the test product.
Storage conditions	Lenses should be stored at room temperature.

Supply	Alcon will provide test lenses. Refer to the MOP for a detailed description.
--------	---

**Table 9–2**      **Comparator Product**

Comparator Product(s)	DAILIES TOTAL1 spherical soft contact lenses (DT1; LID006961)
Manufacturer	Alcon Laboratories, Inc. [name] USA
Indication for Use	The comparator daily disposable contact lenses are indicated for the optical correction of refractive ametropia (myopia and hyperopia) in phakic and aphakic persons with nondiseased eyes with up to approximately 1.5 D of astigmatism that does not interfere with VA.
Product description and parameters available for this study	

• Material: delefilcon A

• Water content: 33%

• Power range: -1.00 to -6.00 D, 0.25 D steps

• Base curve (mm): 8.5

• Diameter (mm): 14.1

Formulation	Please refer to package insert.
Usage	

• Wear:

○ Daily Wear

○ Contralateral

• Replacement period: Daily Disposable

• Exposure: daily for approximately 4 days total duration

• Lens Care: N/A

Number/Amount of Product to be Provided to the subject	Subject will be dispensed study lenses at Visit 1. Spare lens(es) will be provided to the subject.
Packaging description	Blister foil pack

Labeling description	
Lens Foil label includes:
 

- material name and identifier

- base curve

- diameter

- packing solution

- power

- lot number

- expiration date

- content statement

- investigational device statement

- sponsor information

- country of origin

 

• Provided in packages of approximately 40 lenses per power, identified with the following at a min:

- a color coded label stating the protocol number

- material identifier

- power

- an investigational use only statement

- tracking number

Training and/or experience requirements for device	No additional training or experience is required to administer the comparator.
Storage conditions	Lenses should be stored at room temperature.
Supply	Alcon will provide comparator lenses. Refer to the MOP for a detailed description.

More information on the test product can be found in the IB [REDACTED] and more information on the comparator product can be found in the Package Insert for DT1 lenses.

## 9.2 Other Medical Device or Medication Specified for Use During the Study

No other medical devices or medications are required to be used in conjunction with the treatments during the clinical study.

## 9.3 Treatment Assignment / Randomization

Qualifying subjects will be randomized in a 1:1 ratio to receive treatment (lenses) in a contralateral sequence.

Sequence	EDC/randomization integration system	
Sequence 1	LID220365(OD)/LID006961(OS)	
Sequence 2	LID006961(OD)/LID220365(OS)	

Only after signing the ICF, a subject will be assigned a subject number by the electronic data capture system.

[figure not shown]
A randomization list will be generated using a validated system that automates the random assignment of treatment (lens sequence) to randomization numbers in the specified ratio. Subjects will be assigned treatment (lens sequence) according to the randomization list uploaded in the EDC/randomization integration system. The randomization list will be generated and maintained by the study sponsor.

At Visit 1, all eligible subjects will be randomized via the EDC/randomization integration system to one of the treatments (lens sequences). The investigator or delegate will access the respective system after confirming that the subject meets all the eligibility criteria. A randomization number will be automatically assigned to the subject according to the subject randomization list but will not be communicated to the site user. The EDC/randomization integration system will inform the site user of the treatment (lens sequence) assignment to be dispensed to the subject.

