### 3 PROTOCOL SUMMARY

Investigational product type	Device
Study type	Interventional
Investigational products	Test Product: [REDACTED] (LID220365) Comparator Product: DT1 spherical soft contact lenses (LID006961)
Purpose and Scientific Rationale for the Study	In this clinical trial, the overall clinical performance will be assessed for delefilcon A lenses made with a modified manufacturing process.
Objective(s)	
The primary objective of this study is to demonstrate noninferiority (NI) in visual acuity (VA) at distance [REDACTED] [REDACTED] after approximately 4 days of wear.
 
[REDACTED] [REDACTED] [REDACTED]
 
The safety objective is to describe the safety profile of the investigational products.

Endpoint(s)	
Primary Effectiveness
 

Distance VA (logMAR; OD, OS) with study lenses (dispensed power) at Day 4

 
[REDACTED]

	
Safety
 

• Adverse events

• Biomicroscopy findings

• Device deficiencies

Assessment(s)	
Effectiveness
 

• Distance VA (logMAR; OD, OS) with study lenses (dispensed power)

	
Safety
 

• Adverse events

• Biomicroscopy

• Device deficiencies

Study Design	
This is a prospective, randomized, [REDACTED] [REDACTED] double-masked, contralateral, dispensing study evaluating the clinical performance of 2 spherical soft contact lenses. The expected duration of subject participation in the study is approximately 4 days with 2 scheduled visits.

Subject population	
Habitual spherical soft contact lens wearers aged 18 or above, having at least 3 months of contact lens wearing experience, and who wear their habitual contact lenses for at least 5 days per week and at least 10 hours per day.

	
Planned number of subjects enrolled/consented: ~110
 
Planned number of completed subjects: 100
 
[REDACTED]
 
[REDACTED]
									
Sites and Locations	
Planned number of clinical sites: ~ 7
 
Planned locations (initial list of locations, which may change during start up or conduct according to study needs): US
									

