### **7.3 Rationale for Duration of Treatment/Follow-Up**

Subjects will wear test and comparator lenses contralaterally for approximately 4 days. The lenses will be provided by a qualified unmasked study staff member in such a manner that the subject and the investigator remain masked to the lens type. The primary [REDACTED] [REDACTED] will be assessed on approximately the 4th day of wearing both lenses. The duration of using each study product is in accordance with the respective product labeling (see package insert and IB).

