## 9.4 Treatment masking

This study is double-masked, with subjects randomized [REDACTED] to wear contralaterally for the duration of the approximately 4 day treatment period. [REDACTED]

This level of masking will be maintained throughout the conduct of the study. Unmasking will occur only after all planned study data have been validated, and the database locked.

Masked study personnel must avoid seeking information that may compromise masking. Unmasked study personnel must not disseminate information that is potentially unmasking to any masked personnel. The masked and unmasked site personnel must coordinate all study activities as necessary to protect masking and minimize bias during the study.

In the event of a medical emergency where the knowledge of subject treatment is required, an individual investigator will have the ability to unmask the treatment assignment for a specific subject after contacting an appropriate study sponsor representative if time allows.

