## 11.5 Unmasking of the Study Treatment

Masked information on the identity of the assigned medical device should not be disclosed during the study (refer to Section 9.4). If the treatment code needs to be broken in the interest of subject safety, the Investigator is encouraged to contact an appropriate Study Sponsor representative prior to unmasking the information if there is sufficient time. Dependent upon the individual circumstances (i.e., medical emergency), the code may be broken prior to contact with the Study Sponsor. The Study Sponsor must be informed of all cases in which the code was broken and of the circumstances involved. Additionally, the Study Sponsor may be required to unmask the information in order to fulfill expedited regulatory reporting requirements.

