### 12.1 Subject Evaluability

Final subject evaluability must be determined prior to breaking the code for masked treatment (lens sequence) assignment and locking the database, based upon the Deviations and Evaluability Plan (DEP).

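### Does letting the investigator or a delegate open the randomization system undo the investigator's masking?

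*Protocol*

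**What the plan says.** The relevant text is spread over several sections of the protocol.

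- **Section 9.3** (randomization): "The investigator or delegate will access the respective system after confirming that the subject meets all the eligibility criteria". Two sentences later: "The EDC/randomization integration system will inform the site user of the treatment (lens sequence) assignment to be dispensed to the subject". Only the randomization number is withheld from the site user. The sequence table there, repeated in SAP section 1.3, gives a lens identification number for each eye.
- **Section 3** (summary) and the glossary link those numbers to products, for example "Comparator Product: DT1 spherical soft contact lenses (LID006961". The other number, LID220365, is the test lens.
- **Section 7.3**: a qualified unmasked staff member supplies the lenses "in such a manner that the subject and the investigator remain masked to the lens type".
- **Section 9.4** (masking): "Masked study personnel must avoid seeking information that may compromise masking". Unmasked staff must not pass such information on, the two groups must coordinate their work to protect masking, and unmasking waits until the data are validated and the database is locked. Part of this section is blacked out.
- **Section 9.5** (accountability): unmasked delegates hand out the lenses. The following sentence gives the per-subject dispensing and collection records to the investigator or a delegate, without stating masking status.
- **Section 10.2** leaves procedural detail to the manual of procedures (MOP) and delegation of tasks to the investigator.

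**The concern.** Section 7.3 keeps the investigator masked, while 9.3 names the investigator first among those who may open the system that shows the lens sequence. What it shows is not a neutral code. It is a lens number by eye, and anyone holding the protocol can decode it. The record-keeping sentence in 9.5 raises the same question, because a per-subject dispensing record also reveals the sequence.

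The design makes this worth checking. Each subject wears one lens in each eye, and the primary endpoint compares visual acuity between them. A person who knows the sequence knows which eye wears the test lens when acuity is measured and biomicroscopy is graded. The investigator also judges whether adverse events are device-related. Masking is the plan's protection for those judgments.

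There is a reporting question too. Section 12.1 treats the lens sequence as the masked code, to be broken only after evaluability is settled: "prior to breaking the code for masked treatment (lens sequence) assignment and locking the database". Section 11.5 says "Masked information on the identity of the assigned medical device should not be disclosed during the study" and adds "The Study Sponsor must be informed of all cases in which the code was broken and of the circumstances involved". If an investigator saw the sequence in the ordinary course of randomizing a subject, it would be unclear whether that had to be reported as a code break.

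**Working it through.** **Step 1: can every section be satisfied at once?** The table shows each task with its permitted actor and the rule that bears on that choice.

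| Task | Permitted actor | Constraint elsewhere |
|---|---|---|
| Confirm eligibility | Investigator or delegate (9.3) | None; no assignment exists yet |
| Open the randomization system | Investigator or delegate (9.3) | Investigator stays masked (7.3); masked staff avoid unmasking information (9.4) |
| Receive the sequence | Site user (9.3) | Same |
| Hand out lenses | Unmasked delegates only (9.5); unmasked staff member (7.3) | None needed |
| Keep per-subject records | Investigator or delegate (9.5) | Same as for opening the system |

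One allocation meets every row: the investigator confirms eligibility, and an unmasked delegate opens the system, receives the sequence, dispenses and keeps the records. The role already exists, because someone unmasked must know the sequence in order to dispense. The other allocation, in which the investigator opens the sequence screen, fits 9.3 alone but breaches 7.3 and 9.4. The plan as a whole therefore excludes the harmful route, although the sentence in 9.3 does not do so by itself.

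**Step 2: is the display to the investigator established?** Section 9.3 names the investigator or delegate as the person who opens the system, and the site user as the person informed. It does not say that these are always the same person or that every system role sees the sequence. One column of the sequence table is also redacted in the SAP.

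**Step 3: do 11.5 and 12.1 add a contradiction?** Section 11.5 deals with breaking the code for subject safety and with expedited regulatory reporting. Section 12.1 fixes the order of evaluability decisions, unmasking and database lock. Neither governs the routine display of an assignment to the unmasked staff who must dispense it.

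**Step 4: scale.** The inputs are the SD of the paired difference, 0.0567, and the margin, 0.05 logMAR (protocol section 3; SAP section 7); one-sided alpha 0.05; and 100 completers from about 110 enrolled, with 14 to 16 per site (protocol section 8).

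*The plan's own figure.* For a paired t-test with true difference 0 (assumed), the noncentrality is 0.05 / (0.0567/√n). At n = 10 this is 0.05/0.01793 = 2.79 and power is 0.823, so the stated 10 for 80% is reproduced. For 90% power, n = 13 gives 0.911 and the stated 14 gives 0.930.

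*One site's share.* 14/110 = 12.7%; 16/110 = 14.5%. This is the share of subjects whose sequence would be exposed at a site that took the wrong route. It is not a probability that any site would.

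*Room before the margin at 100 completers.* SE = 0.0567/√100 = 0.00567 and t(0.95, 99) = 1.660, so noninferiority is declared when the observed difference is below 0.05 − 1.660 × 0.00567 = 0.0406. From the noncentral t with 99 degrees of freedom and noncentrality (true difference − 0.05)/0.00567:

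| True difference (logMAR) | P(noninferiority declared) |
|---|---|
| 0 | 1.000 |
| 0.02 | 0.9998 |
| 0.025 | 0.997 |
| 0.03 | 0.968 |

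These probabilities assume no bias, so they do not measure the effect of unmasking. They do show that at true differences up to about 0.025 the trial would declare noninferiority anyway, and bias in favour of the test lens would have almost nothing to change. Such bias could matter only if the true difference were near 0.05.

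**The case for a change.** The strongest case for a change is that a protocol should not rely on readers to reconcile its sections. Section 9.3 gives a specific instruction and names the investigator as an equal alternative to a delegate, whereas the rule in 9.4 is general. A coordinator at a busy site may follow the specific sentence. The protocol already has the right term, since 9.5 uses it for dispensing and then drops it one sentence later. Adding it to 9.3 would cost almost nothing, and with a contralateral endpoint the sequence is exactly what an assessor should not know.

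Part of this stands. The wording of 9.3 and of the record-keeping sentence in 9.5 is looser than it could be, and putting the word unmasked before delegate would be a harmless tidy-up.

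The rest does not carry. The general rules are binding, and they point to the one allocation that works. Section 9.4 also lets an investigator unmask a subject in a medical emergency, which only makes sense if the investigator is otherwise masked. The text just before the sentence in 9.4 about maintaining this level of masking is blacked out, and that is where roles would naturally be described, so their assignment cannot be called absent. The MOP may also set them. The sentence in 9.5 about collecting lenses and foils reads as a statement of overall responsibility, and the compliance text in 10.2.3 names no actor.

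**Conclusion.** No change to the plan is called for. This is generic responsibility wording that sites can apply sensibly from the surrounding sections: an unmasked delegate opens the system and keeps the records, and the investigator stays masked as 7.3 requires. Followed as a whole, the plan gives a properly masked comparison. Estimand, sample size and analysis are untouched.

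No effect on error rates is claimed. Exposure would be limited to sites that disregarded 7.3 and 9.4, each holding 12.7% to 14.5% of enrolled subjects. The knowledge would also have to reach whoever measures acuity, and the documents do not identify that person.

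The conclusion rests on two assumptions: that sites apply 7.3, 9.4 and 9.5 together with 9.3, and that neither the redacted part of 9.4 nor the MOP assigns the investigator to the unmasked role. The scale figures further assume the planned SD of 0.0567 and 100 completers.

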## 9.4 Treatment masking

This study is double-masked, with subjects randomized [REDACTED] to wear contralaterally for the duration of the approximately 4 day treatment period. [REDACTED]

This level of masking will be maintained throughout the conduct of the study. Unmasking will occur only after all planned study data have been validated, and the database locked.

Masked study personnel must avoid seeking information that may compromise masking. Unmasked study personnel must not disseminate information that is potentially unmasking to any masked personnel. The masked and unmasked site personnel must coordinate all study activities as necessary to protect masking and minimize bias during the study.

In the event of a medical emergency where the knowledge of subject treatment is required, an individual investigator will have the ability to unmask the treatment assignment for a specific subject after contacting an appropriate study sponsor representative if time allows.

## **9.5 Accountability Procedures**

Upon receipt of the IPs, the investigator or delegate must conduct an inventory. During the study, unmasked delegates must provide the IPs to the subjects in accordance with their randomization assignment. Throughout the study, the investigator or delegate must maintain records of IP dispensation and collection for each subject. This record must be made available to the study monitor for the purposes of verifying the accounting of IP supplies. Any discrepancies and/or deficiencies between the observed disposition and the written account must be recorded along with an explanation. All IPs sent to the investigator must be accounted for by study sponsor personnel, and in no case be used in an unauthorized situation.

The investigator should make every effort to collect unused lenses, foils, and supplies from subjects.

It is the investigator's responsibility to ensure that:

- All study products are accounted for and not used in any unauthorized manner

- All unused products are available for return to the study sponsor, as directed
- Any study lenses associated with a device deficiency or with any product-related adverse event (i.e., ADE or SADE) are returned to the study sponsor for investigation, unless otherwise directed by the sponsor. Refer to Section 11 of this protocol for additional information on the reporting of device deficiencies and AEs and the return of study products associated with these events.

The investigator is responsible for proper disposition of all unused IPs at the conclusion of the study, according to the instructions provided in the MOP.

## **9.6 Changes to concomitant medications, treatments/ procedures**

After the subject is enrolled into the study, the investigator must instruct the subject to notify the study site about:

- Any new medications
- Alterations in dose or dose schedules for current medications,
- Any medical procedure or hospitalization that occurred or is planned
- Any nondrug therapies (including physical therapy and blood transfusions).

The investigator must document this information in the subject's case history source documents.

# **10 STUDY PROCEDURES AND ASSESSMENTS**

## **10.1 Informed Consent and Screening**

The investigator or delegate must explain the purpose and nature of the study, and have the subject read, sign, and date the IRB/IEC-approved informed consent document. The subject must sign the ICF BEFORE any study-specific procedures or assessments can be performed, including study-specific screening procedures. Additionally, have the individual obtaining consent from the subject and a witness, if applicable, sign and date the informed consent document.

The investigator or delegate must provide a copy of the signed document to the subject and place the original signed document in the subject's chart, or provide documentation as required by local regulations.

## **10.2 Description of Study Procedures and Assessments**

Study-specific procedures and assessments described here may include standard of care; other standard of care procedures performed in the clinical management of the subject are not excluded.

Detailed descriptions of assessments and procedures are provided in the MOP. The investigator is responsible for ensuring responsibilities for all procedures and assessments are delegated to appropriately qualified site personnel.

### **10.2.1 Demographics**

Obtain demographic information including age, race, ethnicity, and sex.

### **10.2.2 Medical History and Concomitant Medications**

Collect medical history information for the past year, including information on all medications used within the past 30 days. Include herbal therapies, vitamins, and all over-the-counter as well as prescription medications. Throughout the subject's participation, obtain information on any changes in medical health and/or the use of concomitant medications.

Targeted Medical History and Concomitant Medications will be collected in the eCRF as outlined in the MOP.

